3.2. Rationale for Study Design and Control Groups

This study will evaluate the safety and accuracy of the use of the ¹³C-urea breath test in identifying urease positive organisms in newly diagnosed cases of pneumonia in the ED. Urease producing organisms represent a virulent set of pathogens which may be present in respiratory infections including *Pseudomonas aeruginosa*, *Klebsiella pneumonia* and *Staphylococcus aureus*. Use of the ¹³C-urea breath test may allow for rapid determination of bacteria presence that could provide guidance to future antibiotic selection. In this study, the ¹³C-urea breath test observations will be compared to bacterial identification upon sputum culture.

4. STUDY POPULATION

4.1. Inclusion Criteria

Subjects must meet all of the following criteria to be considered eligible to participate in the study:

Cohort A Only:

1. be a man or woman age 18-70, inclusive
2. have suspected bacterial pneumonia on presentation to the study site based on clinical signs and symptoms
3. be expected to be treated on an outpatient basis in the opinion of the treating clinician at the time of enrollment OR a definitive decision to admit has not been made, and the subject meets ALL of the following criteria; Pulse <125 beats per minute, Systolic blood pressure \geq 100 mmHg, Respiratory rate \leq 24 breaths per minute, Temperature $>$ 35C, and Temperature $<$ 40C. Subjects who are expected to be placed in an ED observation unit are eligible if they meet all of the defined vital sign criteria

Cohort B Only:

4. be a man or woman age 18-85, inclusive,
5. have a diagnosis of suspected bacterial pneumonia on presentation to the study site based on findings of a positive chest x-ray or advanced radiology and clinical signs and symptoms
6. be planned for admission to the hospital ward/floor in the opinion of the treating clinician at the time of enrollment
7. be capable of providing a spontaneous or induced sputum for analysis

Both Cohorts A and B:

8. be capable of completing the breath test according to the clinical judgement of the investigator
9. be able to understand the study procedures, agree to participate in the study program, and voluntarily provide written informed consent

4.2. Exclusion Criteria

Subjects who meet any of the following criteria will be excluded from participating in the study:

1. have a known allergy to urea or any excipient in the nebulized solution
2. be pregnant or have a positive urine pregnancy test
3. have evidence of active oral infection, such as abscess or dense exudate, that requires antibiotic therapy
4. have known diagnosis of cystic fibrosis or bronchiectasis
5. have a known or suspected acute asthma exacerbation on presentation
6. have received treatment with oral or intravenous (IV) antibiotics in the preceding 2 days prior to screening, unless antibiotic failure is suspected

OR

Cohort A Only:

have received treatment with oral or IV antibiotics for > 6 hours prior to breath test

Cohort B Only:

have received treatment with oral or IV antibiotics for > 4 hours prior to breath test

7. have an acute illness or other condition that, as determined by the investigator, would preclude participation in the study

4.3. Discontinuation of Subjects

4.3.1. Procedures for Withdrawal

A subject may be discontinued from the study by the investigator at any time if either determines that it is not in the subject's best interest to continue. Subjects who withdraw consent or who are discontinued from the study before completing all protocol-specified assessments should be evaluated by the investigator before leaving the hospital. The date and the primary reason for discontinuation will be recorded on the subject's case report form (CRF).

4.3.2. Replacement of Subjects

Subjects who do not complete ¹³C-urea nebulization and all scheduled breath sample collection time points may be replaced in this study.

4.4. Lifestyle Guidelines

4.4.1. Confinement

All study related procedures will be performed in the ED or following hospital admission in a single visit lasting less than approximately four hours. The duration of hospitalization following breath test completion for disease management will be at the discretion of the healthcare facility.

4.4.2. Diet

Subjects will not be allowed food or drinks for 15 minutes before the start of nebulization through completion of the final breath sample.

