1. INTRODUCTION

Rapid identification of respiratory pathogens remains a global concern affecting initiation of therapy, and pharmacotherapy selection. The lack of rapid point of care tests that can provide clinicians with some indication of which pathogen(s) is causing disease may lead to selection of inappropriate therapy, in particular to overuse of broad spectrum antibiotics.

Urease producing organisms represent a virulent set of pathogens which may be present in respiratory infections including *Pseudomonas aeruginosa*, *Staphylococcus aureus*, and *Klebsiella pneumoniae*. Identification of the presence or absence of urease activity may allow clinicians to narrow the spectrum of suspected infections, confirming the need for antimicrobial therapy and influencing therapy selection.

The breath test is based upon a modification of existing breath testing technology that detects and monitors a biomarker associated with peptic ulcers. The mechanism of action for detecting urease-containing bacteria in the lungs is the same as for detecting another urease-containing bacterium, *Helicobacter pylori*, in the stomachs of patients with peptic ulcers.

For the intended indication, inhaled ^{13}C -urea will be catalytically hydrolyzed into ^{13}C -carbon dioxide ($^{13}\text{CO}_2$) if urease is present in the bacterial pathogens causing the pneumonia (I).

CO_2 contains predominantly ^{12}C but a small amount of ^{13}C is present. Since the urea is produced with ^{13}C -urea all CO_2 generated by hydrolysis with urease will be $^{13}\text{CO}_2$. By measuring the ratio of $^{13}\text{CO}_2/^{12}\text{CO}_2$ in exhaled breath samples before and after inhalation of ^{13}C -urea, the presence of urease-containing bacteria can be detected. In the absence of urease-containing bacteria in the lungs, the isotopic ratio of $^{13}\text{C}/^{12}\text{C}$ in the baseline and test breath samples will be approximately the same. If urease-containing bacteria are present within the lungs, the concentration of exhaled $^{13}\text{CO}_2$ will be increased measurably in the test breath sample relative to baseline. It is anticipated that urease-producing bacteria can be detected within 5 minutes of initiating the breath test.

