5. TREATMENTS

5.1. Administration of Study Medication

Administration of ^{13}C -urea solution will be completed using an Aerogen Aeroneb Solo nebulizer device, within 60 minutes following reconstitution with 3 mL of sterile water for injection. The solution will be nebulized until the full dose has been administered, with subjects breathing normally through their mouths using the nebulizer mouthpiece. The start and stop time of nebulization will be recorded in the subject CRF. The time nebulization is completed or discontinued will be considered Time 0 for post-dose breath sample collection.

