6.1. Efficacy Assessments

6.1.1. Sample Collection

Baseline breath collection will be completed within 30 minutes prior to nebulization using up to six breath collection bags. Sufficient exhaled breaths to fill the bag will be collected at each defined time point. Breath collection will be by direct exhalation into a bag, or by a breath capture device attached to the nebulizer.

Up to six post-nebulization breath samples will be collected within 10 minutes after completing the nebulized dose, at intervals of 1 minute or greater. Breath collection will be by direct exhalation into a bag, or by a breath capture device attached to the nebulizer.

Samples will be collected within ± 1 minute of the scheduled post-dose time. Actual times will be recorded for all samples as the time of first collected exhaled breath.

Sputum samples will be collected by trained study personnel per standard clinical practice within 15 minutes of the breath test. In brief, subjects will be asked to take several deep breaths and then produce a forceful cough. The subject will be encouraged to expectorate into a sample cup, and the sputum sample will be sent for culture. If the subject has difficulty producing a sputum sample, nebulized saline may be used to loosen secretions and encourage sputum production.

A oropharyngeal swab will be collected per standard clinical practice, and the sample will be preserved for microbiome analysis. A portion of the collected sputum sample will be preserved for microbiome analysis.

Sample collection will be performed according to GCP in a room in the emergency department or Clinical and Translational Sciences Center (adjacent to UNM-ED, Cohort A only).

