6.1.2. Processing of Breath Samples

Breath collection bags will be immediately sealed following collection and labeled with the subject number and collection time point until processed. Breath samples will be centrally processed, and resulting levels will be recorded in the subject CRF.

The breath testing will be performed by Metabolic Solutions, a CLIA accredited laboratory (CLIA ID #30D0970292) at their facility in Nashua, NH. Breath samples from each study subject will be labeled with the de-identified study subject ID, the date and time of collection, and a study ID. The breath samples from a study subject will be shipped overnight via FedEx in an approved and appropriately labeled shipping container. One container is used for each subject and will hold the 300 ml breath bags collected from the subject. Metabolic Solutions will measure the CO₂ concentrations in each bag and also the ¹³CO₂ change over baseline for the post-nebulization breath bags. They will also properly dispose of the breath bags after measurement. The Metabolic Solutions measurements will be tied to the de-identified study

subject ID and collection date/time in the subsequent report sent to the PI for entry into the subject's case report form.

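### The food and drink ban (section 4.4.2) is tied to nebulization, not to the baseline breath (section 6.1.1), so up to 15 minutes are unprotected when baseline is taken early

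*Combined protocol and SAP*

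**What the plan says.** Section 4.4.2 holds the only food and drink rule: "Subjects will not be allowed food or drinks for 15 minutes before the start of nebulization through completion of the final breath sample". It does not mention the baseline breath.

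The timing of the breath samples is set elsewhere:

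- Section 6.1.1, baseline: "Baseline breath collection will be completed within 30 minutes prior to nebulization using up to six breath collection bags".
- Section 6.1.1, after dosing: "Up to six post-nebulization breath samples will be collected within 10 minutes after completing the nebulized dose, at intervals of 1 minute or greater", and "Samples will be collected within ± 1 minute of the scheduled post-dose time".
- Section 5.1: "The time nebulization is completed or discontinued will be considered Time 0 for post-dose breath sample collection". The expected duration of nebulization is not given.

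The result is a difference. Under section 6.1.2 the laboratory reports the ¹³CO₂ "change over baseline for the post-nebulization breath bags". Section 1 gives the premise of the test: without urease-containing bacteria in the lungs, the isotope ratio "in the baseline and test breath samples will be approximately the same".

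Neither the breath test procedures in section 6.4.2 nor the schedule in Appendix A adds a fasting rule. Section 5.10 puts medicines from the previous 7 days on the CRF, but nothing asks for food or drink to be recorded.

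**The concern.** The two rules are anchored to different events. The ban is counted back from nebulization, while the comparison it ought to protect begins at the baseline breath. A subject can give a baseline bag 30 minutes before nebulization, have a snack or soft drink, stop 15 minutes before dosing, and be fully compliant. Another can give an early baseline bag straight after a drink. In both cases something other than urease may differ between the two halves of the comparison.

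The design has little means of correcting this later. All subjects receive ¹³C-urea (section 5.6), so no undosed group shows the background change. Because intake is not recorded, affected subjects cannot be picked out. The same differences feed sensitivity, specificity and predictive values (section 9.2.1), and the findings are meant to help size a later study (section 9.1).

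Intake in this interval is plausible. The setting is an emergency department visit, oral antibiotics may be started before the test within the limits of section 4.2, and section 10.1.3 says the study will not hold up antibiotics. A tablet taken with a drink after an early baseline bag would be an ordinary event.

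**Working it through.** The plan states no figure to reproduce, so the check is timeline arithmetic.

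**Inputs.** Ban starts 15 minutes before nebulization (4.4.2). A baseline bag may be taken at any time t from 0 to 30 minutes before nebulization (6.1.1). The last post-dose bag is at 10 minutes, with a 1-minute tolerance (6.1.1). Nebulization time N is not stated; I assume 3 to 15 minutes.

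**1. Unprotected time between bag and dosing** = max(0, t − 15).

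**2. Guaranteed food-free time before the bag** = max(0, 15 − t).

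| Bag taken t min before nebulization | Intake allowed between bag and dosing (min) | Food-free time guaranteed before the bag (min) |
|---|---|---|
| 30 | 15 | 0 |
| 25 | 10 | 0 |
| 20 | 5 | 0 |
| 15 | 0 | 0 |
| 10 | 0 | 5 |
| 5 | 0 | 10 |
| 0 | 0 | 15 |

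The gap between bag and dosing exists only for t above 15, and its maximum is 30 − 15 = 15 minutes. That is half of the permitted window (15/30), but it is a share of clock time, not of subjects or bags.

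**3. Distance from intake to the post-dose bags.** The latest permitted intake is 15 + N minutes before Time 0: 15 + 3 = 18 to 15 + 15 = 30 minutes. Intake just after a bag at 30 minutes precedes the last scheduled breath by 30 + N + 10 minutes: 43 to 55, or 44 to 56 with the tolerance. Eating immediately before dosing is therefore already barred; what is open is eating between the two measurements.

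**4. After the change.** If the ban starts 15 minutes before the first baseline bag, the first quantity is 0 and the second is at least 15 minutes for every permitted t. With the first bag at t₁, the ban starts t₁ + 15 minutes before nebulization instead of 15, so the added restriction is t₁ minutes: at most 30, and close to none if baseline is taken just before dosing.

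**The case against.** The strongest reply is that the gap is permitted, not required. The 30 minutes are an outer limit. A baseline bag taken 15 minutes or less before dosing leaves no open interval before nebulization, and with up to six bags some may fall inside the ban. The subject must also actually eat or drink in a short interval, and plain water carries no carbon. The documents contain no figure for how intake changes exhaled ¹³CO₂ and section 4.4.2 gives no reason for the ban, so an isotopic purpose is an inference. The study is descriptive, with no formal hypothesis (section 9.3.2), so no sample size or error rate depends on this.

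All of that stands, and it limits the point to a possible disturbance of unknown size and frequency. It does not close the gap. Sample times and the start of nebulization are recorded, so subjects with an early baseline can be identified afterwards, but not those among them who ate or drank.

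A second reply is that the remedy is partial: a meal finished just before the extended ban begins may still be digesting during the test. That is also right and is accepted below.

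**Conclusion.** The mismatch is real and worth correcting. When a baseline bag is taken more than 15 minutes before nebulization, the plan allows up to 15 minutes of unrestricted intake between that bag and dosing, and allows intake immediately before it. Because the readout is a change from baseline, such intake could move it in a subject without urease. This conclusion rests on the section texts alone; only the 18-to-30 and 43-to-56 minute figures depend on the assumed nebulization time.

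A reader might infer more, and the documents do not support it:

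- **That false positives or false negatives will result.** No size of a dietary effect is given and no breath-test positivity threshold is stated, so no misclassification rate can be derived.
- **That the choice of sampling time is distorted.** A disturbed baseline is subtracted from all of a subject's post-dose values and moves them together. Nothing in the documents indicates that intake before dosing would change the time profile over the 10 minutes that follow.
- **That the two sites will differ.** No section describes site routines for food or drink.

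**What to change.** Reconcile section 4.4.2 with section 6.1.1:

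1. Run the restriction from 15 minutes before the first baseline breath sample to the final post-nebulization sample.
2. Record on the CRF any oral intake in that period, with what was taken and when.
3. If intake occurs after baseline, collect a replacement baseline bag before nebulization where the antibiotic-to-test time limit allows. State that replacement bags do not count toward the six-bag limit; otherwise a subject with six bags already filled could not be re-sampled.
4. Where replacement is not possible, flag the subject for a sensitivity analysis.

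**Cost.** A short text change and one CRF item. Subjects go without food or drink for up to about 30 minutes longer, depending on when the first bag is taken. A repeated bag, and any wait before it, uses time within the antibiotic-to-test limit. No extra visit or subject is needed.

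**What it does not do.** It protects the interval from baseline to the last sample and the 15 minutes before it. It does not remove effects of food eaten earlier.

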5. TREATMENTS

5.1. Administration of Study Medication

Administration of ^{13}C -urea solution will be completed using an Aerogen Aeroneb Solo nebulizer device, within 60 minutes following reconstitution with 3 mL of sterile water for injection. The solution will be nebulized until the full dose has been administered, with subjects breathing normally through their mouths using the nebulizer mouthpiece. The start and stop time of nebulization will be recorded in the subject CRF. The time nebulization is completed or discontinued will be considered Time 0 for post-dose breath sample collection.

5.2. Identity of Study Medication

Lyophilized ^{13}C -urea will be provided in 50 mg single-dose vials for reconstitution using 3 mL of sterile water for injection. Inactive ingredients include: Lactose Monohydrate, Tromethamine, and Dilute Hydrochloric Acid (to adjust pH).

5.3. Method of Assigning Subjects to Treatment Groups

All subjects will receive a single 50 mg dose of inhaled ^{13}C -urea.

5.4. Selection of Doses

The dose of ^{13}C -urea has been selected based on clinical use in a subset of subjects. Administration of 50 mg inhaled ^{13}C -urea has been well tolerated in health volunteers and cystic fibrosis patients, while producing detectable levels of $^{13}\text{CO}_2$ in subjects with cystic fibrosis with known bacterial infections (Raissy et al., 2016) (IDE #G120190; unpublished). The safety and efficacy of the administered dose of ^{13}C -urea has also been well tolerated in an evaluation of 97 subjects with and without TB infection in an ongoing study conducted by Avisa Pharma in South Africa (Unpublished, Avisa Pharma).

5.5. Selection of Timing of Dose

Administration of ^{13}C -urea will be conducted prior to, or within 4 hours following, initiation of antibiotic therapy in subjects with a pneumonia diagnosis in the ED. In these subjects it is anticipated that adequate infection burden will be present to produce measurable levels of $^{13}\text{CO}_2$ upon breath analysis within 10 minutes post-nebulization (Raissy et al., 2016). Timing of optimal post-dose breath collection for $^{13}\text{CO}_2$ analysis will be evaluated during this study.

5.6. Blinding and Unblinding of Study Medications

All study participants will receive ^{13}C -urea, no blinding or dummy doses will be utilized in this study.

5.7. Treatment Compliance

Study personnel will oversee administration of ^{13}C -urea while subjects are present in the ED or hospital. The exact date and start and stop times of nebulization will be recorded, as well as the times of post-dose breath collection.

5.8. Drug Accountability

The investigator (or designee) will sign for the investigational product (IP) when it is received. The IP (¹³C-urea) must be handled and stored as described and administered only to those subjects formally entered into the study.

At the completion of the study, and after reconciliation of all delivery and usage records, any unused IP will be returned or destroyed per written instructions.

5.9. Packaging, Labeling, and Storage

¹³C-urea will be provided in single use glass vials for reconstitution prior to nebulization. Non-blinded labels will be utilized for this study, to include product identifier, lot number, expiration, and a disclaimer for investigational use.

Prior to reconstitution, ¹³C-urea will be stored within a range of 15°C to 30°C (59°F to 86°F). Once reconstituted, ¹³C-urea solution will be utilized within 60 minutes.

All study medication will be stored in an area with restricted access. A temperature log or chart will be maintained to monitor the environment.

5.10. Prior and Concomitant Medications

All medications taken by subjects within 7 days prior to receiving ¹³C-urea will be recorded on the CRF. If a medication is started to treat an AE, the medication must be recorded on the Concomitant Medications page of the CRF.

5.11. Concomitant Interventions and Procedures

All interventions or procedures within 7 days prior to receiving the ¹³C-urea, whether diagnostic or therapeutic, will be recorded on the CRF, along with time, date, and reason for the intervention or procedure. If an intervention or procedure is implemented to treat an AE, the event must be recorded on the AE page of the CRF, along with all relevant information.

6. STUDY PROCEDURES

Schedules of study procedures for overall study assessments and day-of-dosing assessments are provided in [Appendix A](#).

6.1. Efficacy Assessments

6.1.1. Sample Collection

Baseline breath collection will be completed within 30 minutes prior to nebulization using up to six breath collection bags. Sufficient exhaled breaths to fill the bag will be collected at each defined time point. Breath collection will be by direct exhalation into a bag, or by a breath capture device attached to the nebulizer.

Up to six post-nebulization breath samples will be collected within 10 minutes after completing the nebulized dose, at intervals of 1 minute or greater. Breath collection will be by direct exhalation into a bag, or by a breath capture device attached to the nebulizer.

Samples will be collected within ± 1 minute of the scheduled post-dose time. Actual times will be recorded for all samples as the time of first collected exhaled breath.

Sputum samples will be collected by trained study personnel per standard clinical practice within 15 minutes of the breath test. In brief, subjects will be asked to take several deep breaths and then produce a forceful cough. The subject will be encouraged to expectorate into a sample cup, and the sputum sample will be sent for culture. If the subject has difficulty producing a sputum sample, nebulized saline may be used to loosen secretions and encourage sputum production.

A oropharyngeal swab will be collected per standard clinical practice, and the sample will be preserved for microbiome analysis. A portion of the collected sputum sample will be preserved for microbiome analysis.

Sample collection will be performed according to GCP in a room in the emergency department or Clinical and Translational Sciences Center (adjacent to UNM-ED, Cohort A only).

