9.4.3. Protocol Violations

All protocol violations and deviations will be identified.

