APPENDIX A. SCHEDULES OF STUDY VISITS AND PROCEDURES

Table 1: Schedule of Study Procedures

Procedure	Screening	Treatment			Follow-Up 48 Hours Post Breath Test
		Pre-Treatment	Nebulization	0-10 Minutes Post-Nebulization	
Informed Consent	X				
Inclusion/Exclusion Evaluation	X				
Demographics and Medical History	X				
Physical Examination	X				
Sputum Collection	X ^b				
Oropharyngeal Swab	X ^b				
Urine Pregnancy Test	X				
Breath Sample Collection		X ^a		X ^a	
Vital Signs	X	X	X	X	
¹³ C-urea Administration			X		
Safety Contact					X
Prior and Concomitant Medication	<----- X ----->				
Adverse Event Monitoring			<----- X ----->		

a Up to 6 samples collected pre- and post-nebulization

b Only required for Cohort B

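### Do unlisted post-dose breath times and a ±1 minute tolerance make the sampling rules in Section 6.1.1 unworkable?

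*Combined protocol and SAP*

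**What the plan says.** Section 6.1.1 places three limits on post-dose breath samples. There may be up to six, taken "within 10 minutes after completing the nebulized dose, at intervals of 1 minute or greater", and "Samples will be collected within ± 1 minute of the scheduled post-dose time". It also says "Sufficient exhaled breaths to fill the bag will be collected at each defined time point" and "Actual times will be recorded for all samples as the time of first collected exhaled breath". Section 5.1 fixes Time 0 as the moment nebulization is completed or stopped.

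On where the schedule is found, Section 6 states "Schedules of study procedures for overall study assessments and day-of-dosing assessments are provided in" Appendix A. Table 1 there has a single column for 0 to 10 minutes after nebulization, with the footnote "Up to 6 samples collected pre- and post-nebulization". No individual times appear.

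Two other places bear on the schedule. Section 4.3.2 says that subjects who do not finish the nebulization and "all scheduled breath sample collection time points may be replaced in this study". Section 9.4.3 says "All protocol violations and deviations will be identified", without mentioning breath times. Section 9.5 presents results at each time point and picks an optimal one. It does not say whether time is nominal or actual.

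**The concern.** A tolerance has meaning only relative to a target, and the targets are not in the document. On its face, nobody can then say whether a given bag was in or out of tolerance, or whether a subject with four bags has completed the schedule and so falls outside the replacement rule. Two sites could answer differently while the study is running.

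The numbers also seem not to fit. Within 10 minutes, five or six windows of ±1 minute leave too little room to guarantee a 1-minute gap between neighbours, so a sample can meet its own tolerance and still break the interval rule or the 10-minute limit. Choosing the best sampling time is a stated objective (Section 2), and the Introduction reports that in the proof-of-concept study values fell rapidly after the first sample at 5 minutes. Loose control of minutes could therefore blur one of the things the study sets out to learn.

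**Working it through.** **Inputs (Sections 5.1 and 6.1.1).** Number of samples k, at most 6; window 10 min from Time 0; minimum interval 1 min; tolerance t = 1 min. The plan states no figure of its own to reproduce.

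**1. Can all three limits be met together?** Take six samples on time at 0, 2, 4, 6, 8 and 10 min. Each interval is 2 min (at least 1), the last sample is at 10 min (not beyond 10), and each deviation from schedule is 0 (within 1). All three hold.

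**2. Where does the apparent misfit come from?** It appears if every sample must be free to use its whole tolerance at the same time. At spacing d, the worst gap between neighbours is d − 2t. Requiring d − 2t ≥ 1 with t = 1 gives d ≥ 3. With the first sample scheduled at Time 0, the last may be as late as 3(k − 1) + 1:

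| k | 3(k − 1) + 1 | Within 10 min? |
|---|---|---|
| 4 | 10 | yes, exactly |
| 5 | 13 | no |
| 6 | 16 | no |

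Equivalently, the largest tolerance usable in full is (10 − (k − 1)) / (2(k − 1) + 1). This is 7/7 = 1.00 min for four samples, 6/9 = 0.67 min (40 s) for five and 5/11 = 0.45 min (27 s) for six. The arithmetic is right, but it rests on an entitlement that Section 6.1.1 does not grant.

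**3. Can staff always obey all three limits in practice?** Use the 2-minute schedule and let a sample scheduled at time s be late by the full minute, at s + 1. The interval rule then allows the next sample from s + 2, which is exactly its scheduled time. So a late sample never forces the next one out of tolerance. At the end of the window, a sample due at 8 min and taken at 9 leaves the last one free at 10, which is still inside the limit. The interval and the window sometimes bind before the tolerance does, and that is all.

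**4. What can be checked afterwards without a schedule?** The interval and the 10-minute limit can both be checked from the recorded times and Time 0. Only the ±1 minute rule needs a list of targets.

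**5. What does the gap do to the analysis?**
- Actual times are recorded (Sections 5.7 and 6.1.1), and laboratory results are reported against collection date and time (Section 6.1.2). Elapsed time is therefore known for each sample.
- Replacement in Section 4.3.2 is permissive. A replaced subject with at least one post-dose sample still meets the mITT definition in Section 9.3.1.
- Section 9.3.2 sets no formal hypothesis, and Section 9.1 plans descriptive analysis. No error rate depends on the schedule.

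**The case for a change.** The strongest argument on the other side is that the omission is a plain fact of the text. Section 6 sends the reader to Appendix A, and the times are not there. Recorded times cannot show a breach of ±1 minute without a target, and a maximum of six does not define completeness for Section 4.3.2. Deviations can also matter to a site: Section 4.13 of the Clinical Monitoring Plan allows termination of a site with frequent unresolved deviations, and Section 10.4 names poor adherence as a ground for stopping. Reading the interval and the window as limits on nominal times would remove the numerical tension, but the text does not say so.

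The missing list stands, and so does the undefined count for completeness. The consequences are weaker. Section 9.4.3 does not refer to breath times, so the link to deviations is an inference. Divergence between sites is possible but not shown. The Clinical Monitoring Plan has site staff trained on procedures (3.3), treats specimen collection times as source data (4.8) and verifies all data against source (4.9). The case report forms, which may carry the nominal times, are not among the documents. The rapid decline seen in the proof-of-concept study is a reason to analyse by recorded time, and the data for that are already collected.

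**Conclusion.** The concern is right that the scheduled times are unlisted and wrong that the limits conflict. Taken together, as written, the three limits can be met with six samples. With five or six, the interval and the 10-minute limit simply narrow the usable part of the ±1 minute.

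What remains is a gap in detail that the sites and the analyst can fill sensibly. Staff keep bags at least a minute apart and inside 10 minutes, and the analyst uses recorded elapsed time or groups samples by nominal time. Either is defensible for a descriptive look at sampling time. Prescribing one of them in Section 9.5 would settle a free choice without saying how a single best time is picked from irregular times, so there is no clear gain. Listing the times would be tidier, but it would add no data and correct no result.

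This conclusion rests on actual times being recorded as Section 6.1.1 requires, on replacement staying optional, and on replaced subjects staying in the mITT set as Section 9.3.1 defines it. On those terms no subject and no sample is lost to analysis, and the plan can stand.
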